## 3. Study Design

### 3.1 Study Design

This is a Phase II, single center open label, study to determine the safety and efficacy of axitinib and avelumab combination in patients with recurrent or metastatic adenoid cystic carcinoma (ACC) with evidence of disease progression within 6 months prior to study enrollment.

Up to 30 patients will be treated with a combination of axitinib 5 mg orally twice a day and avelumab 10mg/kg intravenously every two weeks. A treatment cycle will be 28 days. Treatment will continue until disease progression, death, unacceptable toxicity or consent withdrawal.

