# Proprietary of MD Anderson Cancer Center

EKG	X			
Echocardiogram	X	X 		
Urine analysis for proteinuria	X	X 		
Pregnancy Test (serum or urine) for all women of child bearing potential 	X	X 		
Radiology & Tumor Measurements 	X	X Every 8 weeks, ± 7 days		X
Biopsy	X If archived tissue not available			
Blood-based biomarkers	X 	X 		
Study Drug Compliance		X At each clinic visit		
Subsequent Anticancer Therapy				X
Survival Status				X

1 Written informed consent will be given by each patient prior to undergoing protocol specific evaluation and prior to receiving treatment

2 Chemistry profile includes: BUN, creatinine, sodium, potassium, carbon dioxide, magnesium, total bilirubin, alkaline phosphatase, aspartate aminotransferase, alanine aminotransferase, total protein, and serum phosphorus

3 Serum or urine pregnancy test will be obtained at baseline within 7 days prior to treatment and monthly during treatment in all women of child bearing age and again if clinically indicated

4 CT scan, PET CT scan of the chest/abdomen/pelvis and/or MRI of base of skull/orbit/face as clinically indicated. CT scan or MRI of the brain if clinically indicated

5 Long term follow-up will occur every 6 months by medical/clinical data review or phone contact

6 For patients who discontinue treatment due to reasons other than disease progression, tumor assessment will continue as per during the treatment schedule (i.e. radiology & tumor measurements every 8 weeks +/- 7 days).

7 Extended safety follow up: given the potential risk of immune-related toxicity, safety follow up will be performed up to 90 days after the last dose of avelumab administration. The extended follow up beyond 30 days after last avelumab administration may be performed either via a site visit or via a telephone call with subsequent site visit requested in case any concerns noted during the telephone call

8 Blood will be collected on at baseline (pre-treatment), day 7 (optional), day 15, prior to C3D1, and at progression (optional). Three categories of specimen will be collected: EDTA Vacutainer (checkpoint markers/CAFs): 10 mL = 1 x 10 mL; Streck CF-DNA BCT (ctDNA): 10 mL = 1 x 10 mL; and Sodium Heparin (immunoprofiling): 60 mL = 6 x 10 mL. All blood will be collected and processed by the Thoracic Research Team ([name] laboratory) according the institutional and laboratory standard operating procedures (SOPs).

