### **9. Statistical Consideration**

#### 9.1 Definitions

All efficacy analyses will be performed in all eligible patients enrolled. Safety analyses will be performed on all patients who received any dose of any treatment.

1. Objective Response Rate (ORR) is the percent of patients whose best response is complete response or partial response as determined by RECIST 1.1 criteria.
2. irORR is the percent of patients whose best response is immune-related complete response (ir-CR) or immune-related partial response (ir-PR) as determined by irRECIST criteria.
3. Progression-free survival (PFS) is defined as the duration of time from start of treatment to time of progression or death, whichever occurs first. PFS rate at 6 months is the percentage of patients without disease progression at these time-point.
4. Overall survival (OS) is defined as the duration of time from start of treatment to death. OS rate at 6 months is the percentage of alive patients at these time-point
5. The duration of overall response is measured from the time measurement criteria are met for CR or PR (whichever is first recorded) until the first date that recurrent or progressive disease is objectively documented (taking as reference for progressive disease the smallest measurements recorded since the treatment started).

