# Proprietary of MD Anderson Cancer Center

The above stopping boundaries and operating characteristics are calculated using MultcLean (v.2.1.0) design software downloaded from <http://biostatistics.mdanderson.org/SoftwareDownload>.

Summary statistics including mean, standard deviation, median, and range for the continuous variables, and frequency tables for categorical variables, will be provided. The response rate will be estimated along with its 95% confidence interval. The distribution of time-to-event endpoints including overall survival, progression free survival and duration of response will be estimated using the method of Kaplan and Meier.

The investigator is responsible for completing an efficacy/safety summary report. The efficacy report will be reviewed by the principal investigator and/or study co-chair. For Toxicity monitoring: This will be performed after the first 7 evaluable patients per cohort, complete 1 cycle of study treatment, and every 3 evaluable patients thereafter.

For Response assessment: After the first 10 patients and after 30 patients complete 6 months post-treatment.

A copy of the cohort summary will be placed in the Investigator's Regulatory Binder.

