#### Subjective Progression

Patients requiring discontinuation of treatment without objective evidence of disease progression should not be reported as PD on tumor assessment CRFs. This should be indicated on the end of treatment CRF as off treatment due to Global Deterioration of Health Status. Every effort should be made to document PD even after discontinuation of study treatment.

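### Duration of response has no event for a responder who dies without documented progression, which would usually overstate how long responses last

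*Combined protocol and SAP*

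**What the plan says.** Section 9.1, item 5 starts duration of response when CR or PR criteria are first met and runs it "until the first date that recurrent or progressive disease is objectively documented". Item 3 treats PFS differently: death ends PFS just as progression does. Item 3 then describes the landmark figure in narrower words: "PFS rate at 6 months is the percentage of patients without disease progression at these time-point".

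Section 9.2 states that "time-to-event endpoints including overall survival, progression free survival and duration of response will be estimated using the method of Kaplan and Meier". No censoring rule follows for any of these endpoints, and neither Appendix 1 (RECIST 1.1) nor Appendix 2 (irRECIST) makes death an event for duration of response. Section 2.2 lists the endpoint as a secondary objective.

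Three other places bear on whether such a death can occur:

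- Appendix 1, Subjective Progression: "Patients requiring discontinuation of treatment without objective evidence of disease progression should not be reported as PD on tumor assessment CRFs". It adds: "Every effort should be made to document PD even after discontinuation of study treatment".
- Section 6, footnote 6: "For patients who discontinue treatment due to reasons other than disease progression, tumor assessment will continue as per during the treatment schedule", that is, every 8 weeks within a 7-day window.
- Section 3.1: "Treatment will continue until disease progression, death, unacceptable toxicity or consent withdrawal". This is a list of reasons for stopping treatment, not an analysis rule. It shows only that the plan foresees death as an end distinct from progression.

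**The concern.** The same death on the same day is an event on the PFS curve and not on the duration-of-response curve. A responder who deteriorates clinically, stops treatment and dies before the next scan cannot be recorded as progressed under Appendix 1, and so never reaches the end that item 5 defines. If that patient is censored, Kaplan-Meier treats a dead patient as someone whose response could have continued. The duration reported beside the response rate would then usually look longer than it was. With so few responders, a single patient can carry noticeable weight. Leaving the handling open also means that the choice could be made after the data are seen.

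**Working it through.** **Plan's own figures.** The plan states no figure for duration of response. Its efficacy figures are those of the Simon design in section 9.2, and they reproduce:

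- Early stop: 0.95^10 = 0.599 at a 5% rate and 0.80^10 = 0.107 at 20%.
- Expected size: 10 + 19 × (1 − 0.599) = 17.6 and 10 + 19 × (1 − 0.107) = 27.0.
- Exact type I error 0.0468 and power 0.801, within the stated 0.05 and 0.20 error limits.

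All of these depend on response alone, so the handling of death does not enter.

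**Inputs for the illustration.** The target rate of 20% gives 0.20 × 29 = 5.8 to 0.20 × 30 = 6 responders. The fewest that pass the final rule (more than 3 of 29) is 4. The documents give no times after response, so the exit times below are assumed. The estimator is S(t) = product of (1 − events/at risk). The median is the first time S is at or below 0.5.

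**Six responders, exits at 4, 6, 8, 10, 12 and 14 months, the second by death.**

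| Month | Death counted | Death censored at its date |
|---|---|---|
| 4 | 5/6 = 0.833 | 5/6 = 0.833 |
| 6 | 0.833 × 4/5 = 0.667 | 0.833 |
| 8 | 0.667 × 3/4 = 0.500 | 0.833 × 3/4 = 0.625 |
| 10 | 0.500 × 2/3 = 0.333 | 0.625 × 2/3 = 0.417 |
| 12 | 0.333 × 1/2 = 0.167 | 0.417 × 1/2 = 0.208 |
| 14 | 0 | 0 |

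The median is 8 months counted and 10 months censored. A midpoint convention for the flat stretch at 0.5 gives 9 against 10.

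**Four responders, exits at 4, 6, 8 and 10 months, the second by death.** Counted: 0.75, 0.50, 0.25, 0. Censored: 0.75, 0.75, 0.375, 0. Month 6 is 75% censored against 50% counted, and the median is 8 against 6 months.

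**Does the position of the death matter?** Take the six exits and move the censored death.

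- First exit: S = 0.800 at month 6, 0.600 at month 8 and 0.400 at month 10, so the median is 10.
- Second exit: median 10, as in the table.
- Third exit: S = 0.833, 0.667, 0.667 and then 0.444 at month 10, so the median is 10.
- Fourth, fifth or sixth exit: S has already reached 0.500 at month 8, so the median stays at 8. Only the later curve changes. If the last exit is the death, the curve ends at 0.167 instead of 0.

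**Does the censoring date matter?** Take six responders with progressions at 4, 6, 10, 12 and 14 months and a death at month 7, last scanned at month 5.

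- Death counted: 0.833 at month 4, 0.667 at month 6, 0.500 at month 7.
- Censored at the last scan: 0.833 at month 4, then 0.833 × 3/4 = 0.625 at month 6, with no step at month 7.

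From month 6 to 7 the censored curve is lower (0.625 against 0.667). From month 7 it is higher (0.625 against 0.500).

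**6-month PFS wording.** A literal percentage without progression would count a progression-free death by 6 months as a success, adding 1/30 = 3.3 to 1/29 = 3.4 points each. Read off the Kaplan-Meier curve of PFS as item 3 defines it, such a death is already a failure and nothing is added.

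**The case against.** Item 5 can be read as a deliberate time from response to progression; nothing in the plan promises that death counts. The endpoint is secondary and no decision uses it. Continued 8-weekly scans and the instruction to seek documentation of progression after stopping will capture many of these patients. The times in the illustration are invented, and the death was placed where it moves the median.

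Much of this stands. The safeguards reduce such cases, but cannot remove a sudden death or a death between scans. The median shift does depend on when the death falls. A progression-only endpoint is a possible choice, but Kaplan-Meier with deaths censored does not then describe how long responders actually remain alive and in response.

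Four stronger readings are tempting, and the documents do not support them.

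- A reader might infer that censoring can only ever flatter the curve. That holds for censoring at the death date. The plan names no date, and the last-scan example shows a short interval where the curve is lower.
- A reader might infer that the 6-month PFS rate is also inflated. Item 3's definition of PFS, together with Kaplan-Meier, largely resolves this; what remains is loose wording.
- A reader might try to put a probability on such a death from section 1.4, where 1 of 55 patients died of a cause other than progression. That counts deaths by attributed cause, not by absence of documented progression, and comes from renal cell carcinoma. It gives no useful estimate here.
- A reader might infer that the efficacy conclusion is at risk. The response rate and the accept/reject rule do not use duration of response.

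**Conclusion.** The point holds as a minor defect in a stated definition. Followed as written, item 5 gives a responder who dies without documented progression no event, while item 3 counts the same death for PFS. The textual omission is certain. The direction of the effect rests on the inference that such a patient would be censored.

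Under the assumed six exits with the second by death, month-6 duration of response is 16.7 percentage points higher when the death is censored (83.3 − 66.7 = 16.7), and the median is 2 months longer (10 − 8). A death after the third exit leaves that median unchanged. These figures show what one patient can do; they do not forecast what will happen. If no responder dies without documented progression, nothing changes. ORR, the Simon rule, the sample size and median PFS are unaffected in any case.

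**What to change.** In section 9.1, item 5, define duration of response as the time from first documented CR or PR to documented progression or death from any cause, taking the earlier. State that patients alive and progression-free are censored at their last evaluable tumor assessment. This settles both the missing event and the missing censoring date.

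As a wording alignment only, state the 6-month PFS rate in item 3 as the Kaplan-Meier estimate of being alive and progression-free at 6 months, with a 95% confidence interval.

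The cost is a few phrases. No new data are needed: OS in item 4 already requires the date of death, and section 6 already collects survival status (footnote 5: "Long term follow-up will occur every 6 months by medical/clinical data review or phone contact"). The secondary estimates may come out slightly less favourable.

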## 9.2 Analysis plan

This is a single-arm, phase II trial to assess the efficacy of the combination of axitinib and avelumab in patients with recurrent or metastatic adenoid cystic carcinoma (ACC) with disease progression within 6 months prior to study enrollment. The primary endpoint is the overall response rate by RECIST 1.1. The trial will be conducted by Simon's 2-stage design and the response rate will be estimated after the second stage (Simon, 1989).

It is assumed that the new regimen will have a target overall response rate at 6 months of 20%. A response rate of 5% or lower is considered a failure and the new regimen will be rejected under this circumstance. When the probability of accepting a "bad" regimen (i.e. ORR $\leq$ 5%) is 0.05 and the probability of rejecting a "good" regimen (i.e. ORR  $\geq$ 20%) is 0.20, Simon's Optimal design requires to enter 10 patients in the first stage. If no patient responds to the treatment, the trial will be stopped and the regimen will be declared as ineffective. If there are one or more responses, 19 more patients will be entered in the study to reach a total of 29 evaluable patients. To ensure that we have 29 evaluable patients we will enroll a total of 30 patients. By the end of the study, the new regimen will be rejected if response rate at 6 months is less than or equal to 3/29 and will be accepted otherwise. The operating characteristics of the trial are given as follows. When the true response rate is 0.05 the probability of stopping the trial early is 60%. On the other hand, if the true response rate is 0.20, the probability to stop the trial early is 10.7%. The expected sample sizes are 17.6 and 27.0 when the true response rates are 0.05 and 0.20, respectively.

To ensure patient safety, the toxicity monitoring will be carried out from the 7th patient using the stopping boundaries calculated based on the beta-binomial distribution. The target toxicity rate by the end of cycle 1 (4 weeks of treatment) is 30%. Toxicity is defined as: as adverse events in the first 4 weeks that are judged to be attributable to one agent or both in combination. Relevant hematological events are grade 4 anemia, grade 4 neutropenia lasting longer than 7 days, febrile

neutropenia (absolute neutrophil count  $<1.0 \times 10^9/L$  with temperature  $>38.3^{\circ}C$  on one measurement or  $\geq 38.0^{\circ}C$  for  $>1$  h), grade 3 or worse neutropenic infection, grade 3 or worse thrombocytopenia with bleeding, or grade 4 thrombocytopenia. Relevant non-hematological

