## 1. Introduction

### 1.1 Background and Rationale

Approximately 1,200 new cases of adenoid cystic carcinoma (ACC) occur each year in the United States. ACC is the second most common malignant salivary gland tumor with a recurrence rate following curative intent treatment of 40-50%. ACC is overall chemotherapy-refractory and there is no standard of care treatment for patients with recurrent/metastatic disease, highlighting the urgent need for effective therapy for this patient population. While the majority of patients have indolent metastatic disease, which eventually “accelerates”, approximately 15% have NOTCH1 activating mutations which drives a very aggressive disease phenotype and shorter survival.

VEGF is highly expressed in ACC and its overexpression correlates with tumor aggressiveness. VEGFR inhibitors have shown modest activity in ACC as single agent, rendering response rates of approximately 5 to 10% and disease stability in a large proportion of patients. Given most metastatic ACC have an indolent course, the clinical benefit of disease stability is questionable if disease progression in a pre-specified timeframe is not documented.

In a phase II single arm study including 33 ACC patients, axitinib led to objective responses in 9% of patients, disease stability in 75.8% (30% for more than 6 months), and 67% of patients had tumor shrinkage. In this study, evidence of disease progression by imaging within 6 months of study enrollment or worsening disease-related symptoms was required inclusion criteria.

Immune profiling of ACC samples revealed that most tumors express PD-L2 but have few infiltrating immune cells. Pembrolizumab single agent is being studied in salivary gland carcinomas in a phase 1b trial (Keynote-028) and no responses were seen in ACC.

VEGF-A reduces adhesion molecule expression on endothelial cells, which results in a dysfunctional tumor vasculature and inhibits the infiltration of T cells and other immune cells into the tumor. Several studies have shown an association of tumor angiogenesis or elevated VEGF-A levels with reductions in tumor T cell infiltration. VEGF-A can also suppresses dendritic cell differentiation and activity, increases the expression of checkpoint molecules on CD8 T cells, and modulates the proliferation of regulatory T cells. Treatment of mouse models with VEGFRs inhibitors increases T cell recruitment and infiltration into tumors and can be synergistic with anti-PD1.

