Preliminary safety and efficacy results from an ongoing phase Ib study of axitinib plus pembrolizumab in treatment-naïve patients with renal cell carcinoma have been recently presented. Out of 52 enrolled patients, 35 (67.3%) had an objective response: 2 had complete response and 33 had partial responses; 11 patients had stable disease. Only 10 patients tested positive for PD-L1.

A phase 1b dose-finding study of avelumab and axitinib in patients with advanced renal cell carcinoma revealed the recommended phase 2 dose to be the standard 10 mg/Kg of avelumab intravenously every 2 weeks and axitinib 5 mg per oral twice a day. All 6 patients enrolled had clinical benefit, and five out of six (83%) achieved a partial response (PR). A phase III clinical trial with this combination is ongoing in metastatic renal cell carcinoma (NCT02684006). To put these

results in perspective, in a large phase III trial, axitinib single agent in first line for metastatic renal cell carcinoma rendered an ORR of 32%. Based on this data, we believe that the combination of axitinib and avelumab will be well tolerated and enhance anti-tumor response of axitinib single agent in patients with incurable ACC who are actively progressing. Given the high unmet need, if promising, the results of this trial could lead to a definitive study that can establish the first standard of care systemic therapy for patients with recurrent/metastatic ACC.

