## Proprietary of MD Anderson Cancer Center

axitinib since single agent activity has been reported with this agent in ACC. Guidance for management of the most common overlapping adverse events are outlined below:

- Diarrhea:

Grade 1-2: manage with anti-diarrheal agents (E.g., loperamide). If no improvement dose-reduce/hold axitinib first, if no improvement hold avelumab (management as per Table 4), if improvement, axitinib can be re-started.

Grade  $\geq 3$ : hold both drugs, discard an infectious agent, and treat with anti-diarrheal agents and steroids as per Table 4. Re-start with single agent axitinib.

- Fatigue:

Grade  $\geq 2$ : Hold avelumab first, if no improvement dose-reduce axitinib, if improvement avelumab can be re-started. If only single agent can be tolerated, prioritize axitinib.

- Hypertension

- Hold Axitinib when unable to control blood pressure to  $<140/90$  on greater than 4 Blood pressure medications from multiple classes on maximally tolerated doses.
- Qtc-Hold for  $Qtc > 500$ msec, for  $Qtc$  from 470-499msec, Cardiology collaborator will evaluate and review for drug interactions and presence of underlying structural heart disease, and resume when  $Qtc$  by EKG interpretation shows normal  $Qtc$

- Transaminitis (increase in ALT and/or AST):

Grade 1-2: Hold avelumab first, if no improvement, dose-reduce/discontinue axitinib, if improvement avelumab can be re-started

Grade  $\geq 3$ : hold both drugs, discard an infectious agent, and treat with steroids as per Table 4. Re-start with single agent axitinib.

Other overlapping AEs:

- Decreased appetite, nausea, weight loss, vomiting, dyspnea, arthralgia, stomatitis are more common with axitinib, therefore, dose reductions of these agent should precede avelumab hold.
- Rash, hypothyroidism, asthenia and hematologic toxicities should be initially attributed to avelumab and managed accordingly (Tables 3 and 4), if no improvement by avelumab hold, axitinib dose-reduction/discontinuation should follow.

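### Is a 5% null response rate too low when the protocol itself reports 9% for axitinib alone?

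*Combined protocol and SAP*

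**What the plan says.** Section 9.2 plans a Simon optimal two-stage design with the RECIST 1.1 response rate as primary endpoint. The null is given as "A response rate of 5% or lower is considered a failure and the new regimen will be rejected under this circumstance"; the target is 20%, with error probabilities of 0.05 and 0.20. Ten evaluable patients enter stage 1, and the trial stops if none responds. Otherwise 19 more follow, and the regimen is rejected at 3/29 or fewer responses and accepted above that. Operating characteristics are given at the null and the target only, for example "The expected sample sizes are 17.6 and 27.0 when the true response rates are 0.05 and 0.20, respectively". The section also plans to report the response rate with a 95% confidence interval.

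Section 1.1 gives the background rates. VEGFR inhibitors as single agents in ACC are described as "rendering response rates of approximately 5 to 10% and disease stability in a large proportion of patients". In a single-arm phase II study of 33 patients, "axitinib led to objective responses in 9% of patients", and entry to that study was restricted: "evidence of disease progression by imaging within 6 months of study enrollment or worsening disease-related symptoms was required inclusion criteria". The combination is expected to "enhance anti-tumor response of axitinib single agent in patients with incurable ACC", and "if promising, the results of this trial could lead to a definitive study".

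**The concern.** A null response rate is normally a rate that would not justify further work. If axitinib alone gives about 9%, a combination that also gives 9% has gained nothing from avelumab, yet it lies above the null. Section 9.2 offers no reason for choosing 5%, the bottom of the class range. The protocol relies on axitinib's activity elsewhere: Section 5.4 asks that, for overlapping toxicity, effort be made to continue "axitinib since single agent activity has been reported with this agent in ACC". Section 1.1 also reports no ACC responses to pembrolizumab alone, so a combination that performs like axitinib by itself is a realistic possibility.

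At stake would be the step after this trial. If acceptance were taken to mean that avelumab adds something, a definitive study could be launched on a result that axitinib alone would produce fairly often. A reader given operating characteristics only at 5% and 20% does not see how often.

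**Working it through.** **Inputs.** From Section 9.2: n1 = 10, stop at 0 responses, n = 29, accept at 4 or more, p0 = 0.05, p1 = 0.20. From Section 1.1: 9% of 33 patients, taken as 3 responders (an assumption; the count is not given), and 5 to 10% for the class.

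**Formulas.** With p the true response rate:
- Early stop: PET = (1 − p)^10.
- Expected evaluable patients: EN = 10 + 19 × (1 − PET).
- Acceptance: sum over x = 1 to 10 of P(X1 = x) × P(X2 ≥ 4 − x), where X1 ~ Bin(10, p) and X2 ~ Bin(19, p).

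**The plan's own figures first.**
- At p = 0.05: PET = 0.95^10 = 0.599 (stated 60%). EN = 10 + 19 × 0.401 = 17.6 (stated 17.6). Acceptance = 0.0210 (x = 1) + 0.0183 (x = 2) + 0.0065 (x = 3) + 0.0010 (x ≥ 4) = 0.0468, within the 0.05 allowed.
- At p = 0.20: PET = 0.80^10 = 0.107 (stated 10.7%). EN = 10 + 19 × 0.893 = 27.0 (stated 27.0). Acceptance = 0.2048 + 0.2770 + 0.1984 + 0.1209 = 0.801, so power is at least 0.80.

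An exhaustive search over two-stage designs returns 0/10 and 3/29 as the optimal design for these inputs. Everything 9.2 states reproduces.

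**The same rule at other true rates.** At 9%, PET = 0.91^10 = 0.389, EN = 10 + 19 × 0.611 = 21.6, and acceptance = 0.0930 + 0.0892 + 0.0377 + 0.0088 = 0.2287.

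| True response rate | Probability of acceptance |
|---|---|
| 5% | 0.047 |
| 7% | 0.12 |
| 9% | 0.23 |
| 10% | 0.29 |
| 20% | 0.80 |

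The 0.23 is correct, but it is not the type I error of this design. That is 0.047, at the null the plan states.

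**What acceptance requires.** The 5% is a hypothesised true rate, and the 9% is an observed one. On the observed scale the bar is 4/29 = 13.8%. A result of 3/29 = 10.3%, already above 9%, leads to rejection.

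**How firm the 9% is.** For 3/33 the exact 95% interval is 1.9 to 24.3%, and P(X ≥ 3 | n = 33, p = 0.05) = 0.23. A true axitinib rate of 5% is therefore compatible with that study. Its entry rule also admitted worsening symptoms as an alternative to imaging progression. Section 1.1 does not say whether its responses were confirmed or read blind, whereas this trial requires confirmation at least 4 weeks apart (Appendix 1) and blinded reading (Section 6.1).

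**What a 9% null would cost.** For p0 = 0.09 and p1 = 0.20 with the same error rates, the optimal design is 2/23 then 10/73, and the minimax design is 3/39 then 9/61. That is 73/29 = 2.5 or 61/29 = 2.1 times the planned number, at one center, in a disease that Section 1.1 puts at about 1,200 new US cases a year.

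**The case for a change.** The strongest case for the concern is that the protocol's stated hope is improvement over axitinib, so the rates that matter most for the next decision lie between 5% and 20%, where 9.2 is silent. Acceptance rises about fivefold from 5% to 9% (0.2287/0.0468 = 4.9). The imprecision of 3/33 cuts both ways, since the true axitinib rate could also exceed 9%. Averaged over that uncertainty, acceptance is 0.32 with a Jeffreys prior, 0.37 with a uniform prior and 0.26 with a Beta(0.09, 0.91) prior. Averaged evenly over the 5 to 10% class range it is 0.15. The remedy would cost only a few sentences.

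Part of this stands: 9.2 gives no reason for 5%, and 0.23 is a useful number for anyone planning a follow-on study. But it follows directly from the accept rule, which is fully specified. About 0.25 of the 0.315 Jeffreys average comes from true rates above 10%, outside the protocol's class range, where accepting the regimen is no clear mistake for a screen against 5%. The remaining suggestion, a disclaimer of superiority over axitinib, would withdraw a claim the plan does not make. The planned confidence interval already shows the limits of a bare pass: at 4/29 the exact two-sided 95% interval is 3.9 to 31.7%, which includes 9%.

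**Conclusion.** The concern does not hold. The design tests for activity above 5% in a disease that Section 1.1 describes as having no standard treatment, and for that question it is correct: type I error 0.047, power 0.801, and every stated figure reproduces. The null lies within the protocol's own class range, and the target of 20% is about twice the axitinib estimate (20/9 = 2.2), so the power is placed where a worthwhile gain would lie. The 0.23 acceptance probability at a true 9% is a property of any small screen at an intermediate rate. It shows no fault in the null, the sample size or the rules. Adding a rationale or another operating-characteristic point would leave all of these unchanged, and the conclusion reached by following the plan would be the same. Raising the null is a legitimate alternative, but it is a trade-off against roughly 61 to 73 patients.

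This rests on reading acceptance as the plan defines it, as rejection of 5%. If a report later presented acceptance as evidence that avelumab adds to axitinib, that claim would be unsupported, but the plan contains no such claim. The figures assume 29 evaluable patients, 3 responders behind the 9%, and no early stop under the separate toxicity rule, which could only lower the chance of acceptance.
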